### **9.5.1.3 Modified Rodnan Skin Score**

The mRSS is a validated method for estimating skin thickening. Seventeen different body areas are scored as normal (0), mild thickening (1), moderate thickening (2) and severe thickening (3), with a maximum score of 51. The assessment should be performed by a qualified Investigator (or designee). Except when strictly unavoidable, the same person should perform the assessment at each evaluation during the trial.

A copy of the form for assessing the mRSS is provided in Section [17.3](#).

### **9.5.1.4 American College of Rheumatology-Composite Response Index in Systemic Sclerosis**

Subjects will be evaluated using the ACR-CRISS, an outcome measure for diffuse cutaneous SSc. The ACR-CRISS includes core items that assess change in 2 prominent manifestations of early diffuse cutaneous SSc (skin and interstitial lung disease [ILD]), functional disability (HAQ-DI) and patient and clinician global assessments. In addition, the score captures a clinically meaningful worsening of internal organ involvement requiring treatment.

The ACR-CRISS is a 2-step process that assigns a probability of improvement for a subject that ranges from 0.0 (no improvement) to 1.0 (marked improvement). Step 1 will be evaluated as part of the AE assessment, at which time the Investigator will assess if a subject has developed new or worsening cardiopulmonary and/or renal involvement due to SSc, as outlined below.

- New scleroderma renal crisis, defined as follows (adapted from [Steen et al., 2003](#)):  
[Hypertensive scleroderma renal crisis](#):
  1. New onset hypertension, defined as any of the following:
    - a. systolic blood pressure  $\geq 140$  mmHg
    - b. diastolic blood pressure  $\geq 90$  mmHg
    - c. rise in systolic blood pressure  $\geq 30$  mmHg

d. rise in diastolic blood pressure  $\geq 20$  mmHg

AND

2. One of the following 5 features:

- increase in serum creatinine by  $\geq 50\%$  over Baseline OR serum creatinine  $\geq 120\%$  of ULN for local laboratory
- proteinuria  $\geq 2+$  by dipstick
- hematuria  $\geq 2+$  by dipstick or  $\geq 10$  red blood cells/high-powered field
- thrombocytopenia:  $<100,000$  platelets/mm $^3$
- hemolysis, defined as anemia not due to other causes and either of the following:
  - schistocytes or other red blood cell fragments seen on blood smear
  - increased reticulocyte count

Normotensive scleroderma renal crisis:

1. Increase in serum creatinine  $>50\%$  over Baseline OR serum creatinine  $\geq 120\%$  of ULN for local laboratory:

AND

2. One of the following 5 features:

- proteinuria  $\geq 2+$  by dipstick
- hematuria  $\geq 2+$  by dipstick or  $\geq 10$  red blood cells/high-powered field
- thrombocytopenia:  $<100,000$  platelets/mm $^3$
- hemolysis, defined as anemia not due to other causes and either of the following:
  - schistocytes or other red blood cell fragments seen on blood smear
  - increased reticulocyte count
- Renal biopsy findings consistent with scleroderma renal crisis (microangiopathy)

- Decline in FVC % predicted  $\geq 15\%$  (relative), confirmed by another FVC % within a month, HRCT to confirm ILD (if previous scan did not show ILD) and FVC % predicted  $<80\%$
- New onset of left ventricular failure (defined as ejection fraction  $\leq 45\%$ ) requiring treatment
- New onset of PAH on right heart catheterization requiring treatment
- Gastrointestinal dysmotility requiring enteral (tube feeding) or parenteral nutrition
- Digital ischemia with gangrene, amputation or hospitalization requiring treatment

If a subject meets any of these criteria, the subject is assigned a probability of 0. Otherwise, in Step 2, the probability of improvement is calculated based on the 5 core measures incorporated into the ACR-CRISS, including changes in mRSS, FVC % predicted, HAQ-DI, PTGA and CGA [Khanna and Berrocal et al., 2016].

In addition, the subject will be asked the following ACR-CRISS anchor (additional) questions at the time points indicated in Section 2.1.

Rate the severity of your systemic sclerosis in the last week:

- 0: none
- 1: mild
- 2: moderate
- 3: severe
- 4: very severe

Rate the change in your overall health since you started the trial.

- +3: very much better
- +2: much better
- +1: a little better
- 0: no change
- -1: a little worse
- -2: much worse
- -3: very much worse

Rate the change in your systemic sclerosis since you started the trial.

- +3: very much better
- +2: much better
- +1: a little better
- 0: no change
- -1: a little worse
- -2: much worse
- -3: very much worse

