## 2.1 Schedule of Assessments

	Open-label Treatment Period (Fipaxalparant [HZN-825] 300 mg BID)										Safety Follow-up Visit 11 4 weeks after last dose of fipaxalpar- ant (HZN-825)										
	1	2	3	4	5	6	7	8	9	10											
Trial Visit	1	2	3	4	5	6	7	8	9	10 Trial Week (W)	Day 1	W4	W10^1	W16	W22	W28	W34	W40	W46	W52/PD	Trial Week (W)	Day 1 	W4	W10 	W16	W22 	W28	W34 	W40	W46 	W52/PD
Visit Window (±days)		(±5)	(±7)	(±7)	(±7)	(±7)	(±7)	(±7)	(±7)	(±7)	(±14)										
Informed consent	X																				
Review eligibility criteria	X																				
Weight	X 					X				X											
Fipaxalparant (HZN-825) dispensing	X	X	X	X	X	X	X	X	X												
Compliance		X	X	X	X	X	X	X	X	X											
mRSS 	X 			X		X		X		X											
FVC % predicted/spirometry 	X 			X		X		X		X											
CGA	X 			X		X		X		X											
Lung HRCT	X 									X 											
DLCO	X 					X 				X 											
Patient-reported outcome assessments																					
SHAQ	X 			X		X		X		X											
PTGA	X 			X		X		X		X											
UCLA SCTC GIT 2.0	X 					X				X											
SSPRO-18	X 					X				X											
SScQoL	X 					X				X											
SF-12	X 					X				X											
Pain questionnaire	X 					X				X											
Fatigue (FACIT-F)	X 					X				X											
Raynaud's assessment 	X 				X				X												

	Open-label Treatment Period (Fipaxalparant [HZN-825] 300 mg BID)										Safety Follow-up Visit 11 4 weeks after last dose of fipaxalparant (HZN-825)
	1	2	3	4	5	6	7	8	9	10	
Trial Visit	Day 1 	W4	W10 	W16	W22 	W28	W34 	W40	W46 	W52/PD	
Trial Week (W)		(±5)	(±7)	(±7)	(±7)	(±7)	(±7)	(±7)	(±7)	(±7)	(±14)
Visit Window (±days)											
Anchor questions											
ACR-CRISS (last week)	X 			X		X		X		X	
ACR-CRISS (overall health and change since start of trial)						X				X	
FVC (last week)	X 			X		X		X		X	
FVC (change since start of trial)	X 					X				X	
HAQ-DI (last week)	X 			X		X		X		X	
HAQ-DI (change since start of trial)						X				X	

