16. Blood samples will be collected for serum and plasma biomarkers prior to dosing on Day [REDACTED] as well as at the [REDACTED] Visit.
17. Adverse events occurring or worsening after the first dose of fipaxalparant (HZN-825) on Day 1 through the Safety Follow-up Visit will be considered treatment-emergent adverse events for this trial. All adverse events that occur from the signing of informed consent through the Safety Follow-up Visit will be recorded. The subject should be assessed for the development of new onset of scleroderma renal crisis, new onset of left ventricular failure, new onset of pulmonary arterial hypertension or right heart catheterization requiring treatment, gastrointestinal dysmotility requiring enteral (tube feeding) or parenteral nutrition or digital ischemia with gangrene, amputation or hospitalization requiring treatment.
18. Includes recording of herb/supplement use. See [Table 9.1](#) for restrictions regarding medications.

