Other causes for FVC decline (i.e., respiratory tract infection) should be excluded. Repeat FVC/spirometry should be performed and confirmed prior to initiation of rescue medication if, to the Investigator's clinical judgment, well-founded doubts in the test's quality and the subject's good condition justify the associated delay in subject care, and the increase in risk for the subject.

All concomitant treatment (for diffuse cutaneous SSc and other conditions), including herbs and supplements, must be documented in the eCRF.

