### 9.6.3 Efficacy Endpoint Analysis

All efficacy endpoints will be summarized for the FAS using descriptive statistics, presented by the treatment group subjects were randomly assigned to in HZNP-HZN-825-301 and overall.

A mixed model for repeated measures (MMRM) will be fit to the data *for descriptive purposes* using observed change in FVC % predicted values from all planned post-Trial Baseline assessments (Weeks 16, 28, 40 and 52). The model will include the fixed covariates of: factors used for stratifying randomization (use of mycophenolate mofetil [yes/no] and presence of ILD [yes/no]), treatment the subject received in the previous trial, treatment by Visit Week and Visit Week. The Trial Baseline value will be used as a continuous covariate. An unstructured covariance matrix will be used for the primary analysis; if the model does not converge, other covariance matrices will be considered. The least squares mean (LS mean) difference in change from Trial Baseline to Week 52 from MMRM will be estimated from this model. For subjects with missing data at 1 or more time points, the available data will be included in the analysis.

Exploratory endpoints will be summarized at each time point. Change from Baseline will be evaluated separately for each of the defined Baselines.

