  - e. Renal biopsy findings consistent with scleroderma renal crisis (microangiopathy)
- Decline in FVC % predicted  $\geq 15\%$  (relative), confirmed by another FVC % within a month, high resolution computed tomography to confirm ILD (if previous scan did not show ILD) and FVC % predicted  $<80\%$  predicted;
- New onset of left ventricular failure (defined as ejection fraction  $\leq 45\%$ ) requiring treatment;
- New onset of pulmonary hypertension (PAH) on right heart catheterization requiring treatment.
- Gastrointestinal dysmotility requiring enteral (tube feeding) or parenteral nutrition

- Digital ischemia with gangrene, amputation, or hospitalization requiring treatment

If a subject meets any of these criteria, the subject is assigned a probability of 0. Otherwise, in Step 2, the probability of improvement is calculated based on the 5 core measures incorporated into the ACR-CRISS, including changes in mRSS, FVC % predicted, HAQ-DI, PTGA and MDGA [Khanna et al, 2016].

The predicted probability of improvement for each subject will be computed using the following equation in Step 2 (equation to derive predicted probabilities from a logistic regression model):

$$\frac{\exp(-5.54 - 0.81 * \Delta \text{MRSS} + 0.21 * \Delta \text{FVC\%} - 0.40 * \Delta \text{Pt-glob} - 0.44 * \Delta \text{MD-glob} - 3.41 * \Delta \text{HAQ-DI})}{1 + \exp(-5.54 - 0.81 * \Delta \text{MRSS} + 0.21 * \Delta \text{FVC\%} - 0.40 * \Delta \text{Pt-glob} - 0.44 * \Delta \text{MD-glob} - 3.41 * \Delta \text{HAQ-DI})}$$

where  $\Delta \text{MRSS}$  indicates the change in mRSS from Baseline,  $\Delta \text{FVC\%}$  denotes the change in FVC% predicted from Baseline,  $\Delta \text{Pt-glob}$  indicates the change in PTGA,  $\Delta \text{MD-glob}$  denotes the change in MDGA, and  $\Delta \text{HAQ-DI}$  is the change in HAQ-DI. All changes are absolute change (Time2 – Timebaseline). Subjects missing one or more components of the equation will be classified as non-responders. The MDGA and PTGA are the 11 point scales rating the subject's overall health during the preceding week by physician and patient, respectively.

If a subject does not have an event in Step 1 of the calculation and the equation in Step 2 shows a probability of at least 0.6 for an individual subject at Week 52, that subject will be classified as a responder; otherwise, the subject will be classified as a non-responder.

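### The Step 1 lung criterion of ACR-CRISS and CRISS 25 needs a repeat FVC within a month, but no on-schedule visit supplies one and no rule covers a decline that was never repeated

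*Protocol*

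**What the plan says.** Protocol 9.5.1.4 and SAP 9.2.7 define ACR-CRISS in two steps. Any Step 1 event gives a probability of 0. Otherwise Step 2 computes a probability from five core measures, and the SAP calls 0.6 or more a response. Protocol 9.5.1.5 uses the same Step 1 for CRISS 25.

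The lung item in Step 1 is a relative decline in FVC % predicted of at least 15%, "confirmed by another FVC % within a month, HRCT to confirm ILD (if previous scan did not show ILD"), with FVC % predicted below 80%. On capture, Protocol 9.5.1.4 states that "Step 1 will be evaluated as part of the AE assessment".

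In Protocol 2.1 the row "FVC % predicted/spirometry" is marked at Day 1 and Weeks 16, 28, 40 and 52, and not at the Safety Follow-up Visit. Protocol 9.6.3 agrees, referring to "all planned post-Trial Baseline assessments (Weeks 16, 28, 40 and 52").

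Footnote 17 to that schedule, repeated in the SAP appendix, names renal crisis, left ventricular failure, "new onset of pulmonary arterial hypertension or right heart catheterization requiring treatment, gastrointestinal dysmotility requiring enteral (tube feeding) or parenteral nutrition", and digital ischemia. FVC decline is not in the list. For the PAH item, Protocol 9.5.1.4 requires the finding to be made on catheterization, while the footnote joins the two with *or*. SAP 9.2.7 has "New onset of pulmonary hypertension (PAH) on right heart catheterization requiring treatment".

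The only explicit instruction to repeat is in Protocol 9.4.9: "Repeat FVC/spirometry should be performed and confirmed prior to initiation of rescue medication if" the investigator has well-founded doubts about the test. SAP 9.2.7 says Step 1 events will be adjudicated. SAP 7.4 uses a spirometry retest value where there is one.

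**The concern.** The lung criterion depends on a measurement that the visit plan does not provide. If a site sees a technically sound 15% fall and does not repeat the test, the definition is not met. The subject passes to Step 2, where skin, global and disability scores can outweigh the FVC loss.

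Capture is also weak. Step 1 is collected through adverse event assessment, and the footnote to that assessment leaves out the lung item. Protocol 9.5.3.1.1.1 adds that unequivocal disease progression is reported as an adverse event only if it is serious or is the reason for stopping trial drug. Differences between sites in voluntary retesting could then decide who scores zero.

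At stake are the ACR-CRISS responder rate and the CRISS 25 response proportion, both exploratory.

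**Working it through.** The plan states no figure for this point, so there is none to reproduce.

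**1. Spacing of spirometries.** Inputs: visit weeks and ±7-day windows from Protocol 2.1.
- Weeks 16–28, 28–40 and 40–52: 12 × 7 = 84 days nominal. Shortest gap: 84 − 7 − 7 = 70 days.
- Day 1 to Week 16: 112 days nominal. Shortest gap: 112 − 7 = 105 days.
- With the ±5-day windows in the SAP appendix (based on protocol version 2.2), the shortest gap is 84 − 10 = 74 days.
- After Week 52 no spirometry is planned.

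No two on-schedule tests can therefore fall within a month. A premature-discontinuation visit is the exception, because its date is not fixed.

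**2. Can an unrepeated decline be an ACR-CRISS response?** The SAP 9.2.7 linear predictor is −5.54 − 0.81·ΔmRSS + 0.21·ΔFVC − 0.40·ΔPTGA − 0.44·ΔMDGA − 3.41·ΔHAQ-DI. The SAP's MDGA is the protocol's CGA.

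Constructed subject: FVC 85 to 72, mRSS 28 to 20, PTGA 6 to 4, CGA 6 to 4, HAQ-DI change −0.25.
- Relative FVC decline: 13/85 = 15.3%, ending below 80, so the size conditions of Step 1 are met.
- Predictor: −5.54 + 6.48 − 2.73 + 0.80 + 0.88 + 0.8525 = 0.7425.
- p = exp(0.7425)/(1 + exp(0.7425)) = 0.68, a responder. With a Step 1 event, p = 0.

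Now let baseline FVC be B and the loss exactly 15%. B is an assumption, ranged from 60 to 94; at or above 80/0.85 = 94.1 an exact 15% loss does not end below 80. With the other changes held, the predictor is 3.4725 − 0.0315·B.

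| B | FVC change | p |
|---|---|---|
| 60 | −9.0 | 0.83 |
| 80 | −12.0 | 0.72 |
| 94 | −14.1 | 0.63 |

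If only mRSS and FVC change, the mRSS fall needed for p ≥ 0.6 is (ln 1.5 + 5.54 + 0.0315·B)/0.81. That is 9.7 points at B = 60 and 11.0 at B = 94, against 7.3 with no FVC change. Step 2 penalises the FVC loss but does not rule out a response.

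**3. Can it be a CRISS 25 response?** In the same subject mRSS falls 8/28 = 28.6%, and PTGA and CGA each fall 2/6 = 33.3%. Three components pass the 25% improvement threshold, and only FVC worsens. The rule needs at least two improved and allows one worsened, so the subject responds. A Step 1 event would make this a non-response.

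**4. Do the existing provisions cover it?** The repeat in Protocol 9.4.9 is conditional and concerns rescue medication. Its 10-point absolute FVC criterion is not reached by a 15% relative loss when B is below 10/0.15 = 66.7. SAP 7.4 selects a retest but requires none. SAP 9.2.7 adjudicates Step 1 events without saying what happens to an unrepeated decline. The lung item also does not say which of the two Baselines the 15% is measured from.

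**The case against.** A reader might infer that the lung criterion can almost never trigger. The documents do not support that. Protocol 9.5.1.4 itself implies an event-triggered repeat, and such a repeat need not appear in a visit schedule; right heart catheterization and renal biopsy are in Step 1 and are not scheduled either. Unscheduled spirometry is allowed, SAP 7.4 expects retests, and a premature-discontinuation visit can fall within a month of the previous test. The full criterion stands in 9.5.1.4, and nothing says that sites work only from footnote 17. Central over-reading puts the FVC values in the database whatever is reported as an adverse event.

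A reader might also infer a sizeable upward bias. The example is one constructed subject who also needs clear improvement elsewhere, and no frequency can be derived.

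That CRISS 25 tolerates one worsened component is the index's own definition, not a flaw in this plan. The PAH differences may be slips: the SAP keeps the catheterization condition, and its abbreviation list expands PAH as pulmonary hypertension. The wording needs reconciling, but the documents do not show that it changes any subject's score.

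Finally, counting every unconfirmed last-visit decline in the main analysis would drop a confirmation that the definition requires.

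These points limit the claim. They do not supply a rule for the unrepeated decline, and adjudication helps only for cases that reach the adjudicators.

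**Conclusion.** The concern holds in limited form. The lung item in Step 1 depends on a confirmation that no on-schedule visit provides, that 9.5.1.4 only implies, and that footnote 17 does not prompt. The SAP has no rule for a qualifying decline that was never repeated, and such a subject can be counted as a responder on both indices.

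The direction is known: a missed Step 1 event can only raise a responder rate. The size is not known, because the documents give no rate of 15% declines or of voluntary retesting. The effect on differences between the prior-treatment groups could go either way. The p values rest on assumed changes in the other components and an assumed baseline FVC of 60 to 94.

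The affected endpoints are exploratory, in an open-label trial analysed descriptively. The primary change in FVC % predicted does not depend on Step 1. This merits a correction before database lock but does not threaten the trial's main result.

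**What to change.** 1. Reconcile footnote 17, in the protocol and the SAP appendix, with Protocol 9.5.1.4 so that it lists every Step 1 criterion, including the FVC item. Align the PAH wording across 9.5.1.4, footnote 17 and SAP 9.2.7.
2. In SAP 9.2.7, identify by program every relative decline of at least 15% to below 80% in the centrally over-read spirometry, separately for each Baseline. Send all of them to the planned Step 1 adjudication instead of relying on adverse event reports. Do the same in the CRISS 25 derivation, which has yet to be added because the SAP was written to protocol version 2.2.
3. Keep the one-month confirmation as the main definition. Add a sensitivity analysis that also counts unrepeated declines as Step 1 events if they persist at the next scheduled spirometry or occur at the subject's last spirometry. State how the HRCT condition is read there, since scans are scheduled only at Day 1 and Week 52. Report how many subjects change status on each index.

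The cost is a footnote correction, some SAP text, and a little more programming and adjudication. No visit, procedure or treatment decision changes. The responder rate in the sensitivity analysis may be slightly lower, partly because an occasional transient fall at the last visit will count as an event.

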### 9.5.1.5 Revised Composite Response Index in Systemic Sclerosis (CRISS 25)

The Revised CRISS (CRISS 25) is defined as improvement in at least 2 components:  $\geq 5\%$  increase for FVC % predicted and/or  $\geq 25\%$  decrease for mRSS, HAQ-DI, PTGA, CGA and worsening in no more than one component:  $\geq 5\%$  decrease percent predicted FVC and/or  $\geq 25\%$  increase for mRSS, HAQ-DI, PTGA, CGA, at 52 weeks. Revised CRISS (CRISS 25) is also a 2-step process. If the subject meets Step 1 (as defined in Section 9.5.1.4), they are considered

not improved, given a percentage change of 0% for each core set item. In Step 2, the five core set measures are individually collected and scored.

#### **9.5.1.6 Plasma and Serum Biomarkers**

Blood samples will be collected prior to dosing on [REDACTED] as well as at the [REDACTED] Visit for analysis of plasma and serum biomarkers associated with the LPAR1 pathway, inflammation or fibrosis. Only subjects who were able to provide a Baseline blood sample in Trial HZNP-HZN-825-301 for serum and plasma biomarkers will have this assessment completed.

Examples of biomarkers that may be measured include, but are not limited to, proteins associated with the complement pathway and components of extracellular matrix pathways.

Instructions for processing, handling, storing and shipping of samples will be detailed in the laboratory manual that will be provided to each site. Samples will be collected, processed and stored at  $\leq -70^{\circ}\text{C}$  at the site until shipment to the central laboratory (PPD Central Laboratory). The central laboratory will store the samples at  $\leq -70^{\circ}\text{C}$  until shipment to the appropriate laboratory for testing. Based on the results of the above assays, other similar serum biomarkers may be assayed to further explore drug and disease mechanisms. Blood samples collected for analysis of biomarkers may be used for future testing should there be new information about the disease; however, the samples will not be stored for more than 5 years after the trial is completed. All samples will be destroyed after all potential biomarkers have been evaluated or 5 years after the trial is complete, whichever comes first.

#### **9.5.1.7 Lung High-resolution Computed Tomography**

Lung HRCT will be reviewed by a central reader.

#### **9.5.1.8 Diffusing Capacity of the Lungs for Carbon Monoxide**

The site will use its own DLCO equipment and conduct all measurements with the same DLCO equipment in case that several devices are available at the site. Single-breath DLCO measurement will be carried out according to the ATS guideline on DLCO measurements when possible [Graham et al., 2017].

DLCO values will be adjusted for the most recent hemoglobin value. The DLCO assessment should always be performed after the FVC measurement and should always be started approximately the same time each day.

#### **9.5.1.9 Patient-reported Outcome Assessments**

A copy of each assessment is provided in the Appendix (Section 17).

